4.2 Exclusion Criteria

Patients who meet any of the following criteria will be excluded from the study.

- 1. Histologic variants other than adenocarcinoma in the primary tumor
- 2. Abnormal liver functions consisting of any of the following:
 - a) Serum bilirubin $\ge 1.5 \text{ x ULN}$

b) AST and ALT $> 2.5 \times ULN$

- 3. Therapy with other hormonal therapy, including any dose of Ketoconazole, finasteride (Proscar), dutasteride (Avodart) any herbal product known to decrease PSA levels (eg, Saw Palmetto and PC-SPES) within 4 weeks of study drug.
- 4. Requirement for corticosteroids greater than the equivalent of 7.5 mg of prednisone daily.
- 5. Therapy with samarium or strontium within 8 weeks prior to first dose of study drug.
- 6. Active infection or concomitant illness that is not controlled with medical management.
- 7. Prior radiation therapy completed < 4 weeks or single fraction of palliative radiotherapy within 14 days prior to first dose of study drug.
- 8. Any "currently active" second malignancy, other than non-melanoma skin cancer. Patients are not considered to have a "currently active" malignancy, if they have completed therapy and are considered by their physician to be at least less than 30% risk of relapse over next 3 months.
- 9. Active psychiatric illnesses/social situations that would limit compliance with protocol requirements.
- 10. Active or uncontrolled autoimmune disease that may require corticosteroid therapy during study
- 11. Severely compromised immunological state, including being positive for the human immunodeficiency virus (HIV)
- 12. Acute or chronic hepatitis B or C
- 13. Chemotherapy and other investigational therapies (targeted or immunotherapy) will require a 4-week washout period before treatment initiation
- 14. Initiation of bisphosphonate therapy within 4 weeks prior to first dose of study drug. Patients on stable doses of bisphosphonates that show subsequent tumor progression may continue on this medication; however, patients are not allowed to initiate bisphosphonate therapy during the study.
- 15. Impaired cardiac function or clinically significant cardiac diseases, including any of the following:
 - a. History or presence of serious uncontrolled ventricular arrhythmias or presence of atrial fibrillation
 - b. Clinically significant resting bradycardia (< 50 beats per minute)

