5.3 Restrictions

5.3.1 Patients must be instructed not to take additional medications including overthe-counter products and herbal/alternative medications during the study without prior consultation with the investigator. It is important to avoid concomitant medications that are known to cause hepatotoxicity.

Oral contraceptives are generally metabolized by CYP3A4/2C9, and act also as a moderate inhibitor of CYP1A2, therefore should not be used. Thus, patients who are sexually active and are using oral contraceptives as a method of contraception, should change to two highly effective contraceptive methods during the study participation.

Permitted treatments during the study include, but are not limited to the following:

- Pain medication to allow the patient to be as comfortable as possible
- Localized radiotherapy and treatment with bisphosphonates for pre-existing, painful bone metastases is permitted only if evidence of radiological progression is not present. Treatment with bisphosphonates must begin before the study treatment is initiated.
- Nutritional support or appetite stimulants (e.g. megestrol)
- Oxygen therapy and blood products or transfusions
- Prophylactic anti-emetics are allowed for patients who, at the discretion of the investigator, have experienced ≥ grade 1 nausea or vomiting.
- Hematopoietic growth factors should be used according to the guidelines established by the American Society of Clinical Oncology (ASCO) or as dictated

by local practice. The ASCO guidelines are available [http://jco.ascopubs.org/cgi/content/full/24/19/3187]

The administration of anticoagulation and antiaggregation agents (e.g. eptifibatide, epoprosterol, prasugrel, dipyridamole, fondaparinix) should be allowed except prasugrel, due to its potential drug-drug interaction with either sorafenib or TKI258. Prasugrel is primarily metabolized by the CYP3A4 and CYP2B6 and to a lesser extent by the CYP2C9 and CYP2C19. Co-administration of prasugrel with sorafenib could increase the systemic exposure of parsugrel, since sorafenib could inhibit CYP2B6. In addition, in vitro study demonstrated that TKI258 is an inducer of CYP2C9 and CYP2C19, co-administration of TKI258 with parsugrel is likely to reduce the exposure of parsugrel. For oral anticoagulants, the upper limit of INR is < 1.5.

The following concomitant treatments are not allowed during the study:

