- Concurrent use of isoniazid, labetolol, trovafloxacin, tolcapone, and felbamate are not permitted, since alternative less hepatotoxic drugs are available to use.
- Concurrent use of other investigational drugs is not permitted.
- The administration of other antineoplastic therapy (e.g. chemotherapy, hormone therapy, immunotherapy, targeted therapy, monoclonal antibodies and radiation therapy) is not permitted. Patients requiring radiation therapy after the start of the study are considered as having progression of disease and must discontinue study treatment.

5.3.2 Concomitant therapy with the following is **prohibited**:

- Chemotherapy
- Multifraction radiation therapy
- Immunotherapy
- Radiopharmaceuticals such as strontium (⁸⁹Sr) or samarium (¹⁵³Sm)

Patients who require the use of any of these therapies will be discontinued from study-treatment, entered into long-term follow-up for overall survival assessments. Patients who discontinue from the study will be followed for safety outcomes for **30 days** following the patient's last dose or until the patient receives another anticancer therapy, whichever occurs first.

5.3.3 Concomitant therapy with the following is **restricted**:

- 5 α -reductase inhibitor
- Ketoconazole, diethylstilbestrol, PC-SPES, and other preparations such as saw palmetto thought to have endocrine effects on prostate cancer
- Potent inhibitors/inducers of the following CYP450 enzymes including quinidine (a CYP2D6 inhibitor), fluvoxamine (CYP1A inhibitor), omeprazole (a CYP1A inducer), ketoconazole, itraconazole, erythromycin and glibenclamide (CYP3A4 inhibitors), as well as phenobarbital, phenytoin, carbamazepine and rifampicin (all CYP3A4 inducers), should be

used with caution. A comprehensive list of medications that inhibit, induce, and/or are metabolized by the various CYP 450 enzyme isoforms can be found at http://medicine.iupui.edu/flockhart. See also, Appendix H.

The decision to administer a restricted therapy should be made based on the consideration of the safety of study participant. Such therapies will be used with careful monitoring.

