6.5.6 Expectedness

Management of Symptoms Related to Castration

Treatment with androgens, estrogens, and progestin to control hot flushes is not allowed. Antidepressants are permitted for the management of hot flashes. Selective serotinin reuptake inhibitors (SSRIs) are also permitted.

Management of Persistent and Refractory Toxicity

Utilizing the NCI CTCAE (version 3.0), events which are moderate and interfere with function that are not consistent with a patient's medical history, and are refractory to medical treatment, should be investigated carefully to ensure that no other etiology is present. Study drug will be held for any toxicity events deemed definitely, probably, or possibly drug-related (such as diarrhea, hypertension, vomiting, diarrhea, and dizziness) and that are greater than grade 2. Drug will be held until severity is reduced to Grade 1 or less and then resumed daily dosing with a dose reduction of 1 capsule as outlined in section 5.2. Up to 2 dose reductions, ie, $5 \rightarrow 4$ capsules, $4 \rightarrow 3$ capsules, are allowed as outlined in section 5.2. Patients with toxicities that fail to resolve to \leq Grade 1 within 21 days will be taken off study.

Management of All Other Toxicities

Other toxicities may occur. Supportive care should be prescribed as needed. They may also be prescribed prophylactically to prevent toxicity from developing or recurring. The examples include anti-emetics for nausea/vomiting, analgesics for pain, antipyretics for fever and antidiarrheals for diarrhea. Because long-term

androgen deprivation may lead to metabolic diseases, such as glucose intolerance, hypercholesterolemia, osteoporosis, and anemia, appropriate medication may be prescribed.

Abnormal laboratory values will be only be captured as adverse events if deemed "clinically significant" by the investigator.

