6.8 Concomitant Medication Assessments

Supportive care medications are permitted with their use following institutional guidelines. For patients who did not undergo orchiectomy, concurrent treatment with LHRH analogue is mandatory and must be recorded.

The concurrent administration of other anticancer therapy, including cytotoxic, hormonal (except LHRH agonists), or immunotherapy is prohibited during study

treatment phase. Use of other investigational drug therapy for any reason is prohibited.

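### Section 5.3.3 allows hormonally active agents under monitoring while 5.3.1, 6.8, 6.10 and 8.0 bar hormonal anticancer therapy, and Section 10 has no rule for PSA values after such use

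*Combined protocol and SAP*

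**What the plan says.** **Concomitant treatment.** Section 5.3.3 lists 5-alpha-reductase inhibitors as restricted and, in a separate bullet, "Ketoconazole, diethylstilbestrol, PC-SPES, and other preparations such as saw palmetto thought to have endocrine effects on prostate cancer". On how restricted agents are used it says "The decision to administer a restricted therapy should be made based on the consideration of the safety of study participant", and then "Such therapies will be used with careful monitoring".

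The not-allowed list in Section 5.3.1 says: "The administration of other antineoplastic therapy (e.g. chemotherapy, hormone therapy, immunotherapy, targeted therapy, monoclonal antibodies and radiation therapy) is not permitted". Section 6.8 rules out other anticancer therapy, "including cytotoxic, hormonal (except LHRH agonists), or immunotherapy is prohibited during study" treatment; 6.10 and 8.0 repeat this. Section 8.0 adds that a patient who receives a prohibited drug will be discontinued from protocol treatment, although the section opens by saying only that the investigator may withdraw a patient. The list headed prohibited in 5.3.2 does not mention hormonal agents.

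**Entry.** Exclusion 3 bars other hormonal therapy within 4 weeks of study drug. It names ketoconazole at any dose, finasteride and dutasteride, together with "any herbal product known to decrease PSA levels", for which it gives saw palmetto and PC-SPES as examples. Inclusion 6 requires DES to be stopped at least 4 weeks beforehand. Section 1.2 describes ketoconazole and DES as further antiandrogen therapy, used when PSA or clinical disease progresses on LHRH treatment.

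**Outcome.** Section 10.0 makes early response, measured by a drop in PSA under working-group criteria, one of two primary outcomes. It has no provision for PSA values obtained after another PSA-active agent is started.

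**The concern.** At entry the protocol removes these agents because it regards them as hormonal or PSA-lowering. During treatment, the period in which the PSA outcome is measured, one section lets them back in and four others bar them when they count as hormonal anticancer therapy. A physician who follows 5.3.3 would keep the patient on TKI258 and go on collecting PSA; one who follows 8.0 would take him off protocol treatment.

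The trial has a single arm, so no control group shows how much of a PSA fall comes from a second agent. Any such fall would be credited to TKI258. The error would also carry into the correlation of PSA modulation with bone remodeling markers, which is part of the primary objective, and into the logistic models for the probability of PSA response.

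The situation can plausibly arise. Under Sections 6.9.1 and 10.0, PSA progression alone does not force withdrawal, so a patient with rising PSA can stay on study while 5.3.3 leaves room to add one of these agents.

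**Working it through.** The plan states no PSA response target, power or PSA-based sample size, so there is no figure to reproduce. The check is mainly a comparison of sections.

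**Step 1. Each agent's status, on study and at entry.**

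| Agent | Status under 5.3.3 | How the protocol describes it elsewhere | Entry rule |
|---|---|---|---|
| 5-alpha-reductase inhibitors | Restricted | Hormonal therapy (Exclusion 3: finasteride, dutasteride) | None within 4 weeks |
| Ketoconazole | Restricted, in both the endocrine and the CYP450 bullets | Hormonal therapy at any dose (Exclusion 3); antiandrogen (Section 1.2) | None within 4 weeks |
| DES | Restricted | Synthetic estrogen, antiandrogen therapy (Section 1.2) | Stopped at least 4 weeks before (Inclusion 6) |
| PC-SPES, saw palmetto | Restricted | PSA-lowering herbal products (Exclusion 3) | None within 4 weeks |

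**Step 2. Apply the prohibitions.** On the protocol's own classification, every row is hormonal or PSA-lowering. Sections 5.3.1, 6.8, 6.10 and 8.0 bar hormonal treatment given against the cancer. When one of these agents is given with that effect in view, 5.3.3 says it may be used with monitoring and 8.0 says treatment ends. No text says which section prevails.

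**Step 3. Apply Section 10.** The stated criterion for giving a restricted agent is participant safety; whether PSA can still be interpreted is not part of it. Section 10.0 does not censor later PSA values, class the patient as a non-responder or call for a sensitivity analysis. As written, a qualifying PSA fall counts whatever caused it.

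**Step 4. Size.** With N = 40 (Section 10.0), one falsely counted responder moves the rate by 1/40 = 0.025, or 2.5 percentage points.

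To go from users to false responders, let c be the share of patients using such an agent, p the PSA response rate on TKI258 alone, and q the rate among users, with q above p:

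- observed rate = (1 − c)p + cq
- inflation = c(q − p)
- extra apparent responders = 40c(q − p)

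The documents give none of c, p or q; all values here are assumptions.

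- Example: p = 10%, c = 10%, q = 50%. Observed rate = 0.90 × 0.10 + 0.10 × 0.50 = 0.14. Inflation is 4 points, or 40 × 0.04 = 1.6 extra responders.
- Low end: p = 20%, c = 5%, q = 30%. Inflation = 0.05 × 0.10 = 0.5 points, or 0.2 responders.
- High end: p = 5%, c = 20%, q = 50%. Inflation = 0.20 × 0.45 = 9 points, or 3.6 responders.

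**The case against.** **Purpose of use.** The strongest reply is that the bans cover hormonal drugs used as anticancer treatment, while 5.3.3 covers incidental use, such as ketoconazole as an antifungal or a 5-alpha-reductase inhibitor for benign disease. The conflict would then shrink to a missing clause on purpose. The bans do carry that qualifier, so the point stands in part. But the protocol never states this division. Section 5.3.3 defines the second bullet by endocrine effect on prostate cancer and puts ketoconazole there as well as in the drug-interaction bullet, and Exclusion 3 bars ketoconazole at any dose. Even if the reading is accepted, PSA stays exposed, because Section 10 does not address incidental use either.

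**Safeguards.** Section 5.3.1 requires patients to consult the investigator before taking any additional medication, including over-the-counter and herbal products. Section 7.4.1 has concurrent medications and PSA assessed every 4 weeks. These limit unrecorded use and make an analysis rule workable. They do not resolve the conflict, since the investigator consulted is the person faced with it.

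**No decision uses PSA.** This is correct. The formal criterion in Section 10.0, Pr(mE > mH | data) > .95, uses survival only, and there is no PSA stopping rule.

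**Stronger readings that the documents do not support.**

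- A reader might picture one site following 5.3.3 and another following 8.0. The title page and Section 4.0 describe a single site; the divergence can only be between treating physicians or between patients.
- A reader might add that permitting megestrol in 5.3.1 contradicts 6.5.6, which says "Treatment with androgens, estrogens, and progestin to control hot flushes is not allowed". The indications differ (appetite and hot flushes), and nothing in the documents says that megestrol lowers PSA.
- A reader might treat the absence of hormonal agents from 5.3.2 as permission. It is not, because the not-allowed list just before it already names hormone therapy.
- A reader might claim an inflation of 5 to 10 points. That needs 2 to 4 false responders. In the example above each user adds q − p = 0.40 of a responder, so it would take 2/0.40 = 5 to 4/0.40 = 10 users, or 12.5% to 25% of 40 patients. Nothing in the documents points to use on that scale.

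**Conclusion.** The inconsistency is real and worth correcting. The same agent can be allowed or treatment-ending depending on the section read, and the analysis plan would count the resulting PSA fall as TKI258 response. The possible bias is upward in the PSA response estimate, and it can also distort the PSA and bone-marker correlation and the logistic models. The survival-based conclusion is untouched.

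The only size that follows from the documents is 2.5 percentage points per falsely counted responder. The 0.5 to 9 point range rests wholly on assumed values of c, p and q, and if no patient uses these agents the bias is zero. The working-group response criteria are cited rather than reproduced, so it cannot be checked here whether they deal with added agents; the plan's own text does not.

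**What to change.** 1. Reconcile 5.3.1, 5.3.2, 5.3.3, 6.8, 6.10 and 8.0 so that each agent listed in 5.3.3 has one status, with any distinction by purpose of use written down. Which status applies is for the sponsor to decide.
2. Add one sentence to Section 10: PSA values obtained after the start of any such agent do not count toward PSA response, with start dates taken from the concurrent-medication data already collected every 4 weeks. Say that the patient stays in the denominator and is classified on his earlier values, and that the bone-marker correlation uses the same cut-off.

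A sensitivity analysis that keeps all PSA values would show how much the rule matters.

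The cost is a protocol clarification and a sentence in the analysis plan, with no new data collection. The reported response rate may be slightly lower, because a true TKI258 response that first appears after such an agent is started would not be counted.

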5.4 Treatment Compliance

The investigator must keep an accurate accounting of the number of investigational capsules received from Novartis, dispensed to the patients, the number of units returned to the investigator by the patient, and the number of units returned to Novartis during and at the completion of the study. The study drug must be dispensed only by an appropriately qualified person to patients in the study. The drug is to be used in accordance with the protocol by patients who are under the direct supervision of an investigator.

5.5 Packaging and Labeling

TKI258 100 mg is supplied as a hard gelatin capsule/tablet. The capsules will be provided in either blisters or bottles. TKI258 medication labels will comply with the legal requirements of each country and be printed in the local language. The inactive ingredients for the dovitinib capsules are pregelatanized starch, colloidal silicon dioxide, microcrystalline cellulose, and magnesium stearate.

5.6 Storage and Accountability

The study drug must be stored in a secure area, limited access area. The storage conditions are described on the medication label. It will be administered only to patients entered into the clinical study, at no cost to the patient, in accordance with the conditions specified in this protocol. The capsules/tablets should be stored according to the label in a secured, limited access area until required.

5.7 Investigational Product Retention at Study Site

The study site must maintain accurate records demonstrating dates and amount of study treatment received, to whom dispensed (patient by patient accounting), and accounts of any study treatment accidentally or deliberately destroyed. At the end of the study, reconciliation must be made between the amount of study treatment supplied, dispensed, and subsequently destroyed or returned to Novartis or its representative.

6.0 STUDY PROCEDURES

6.1 Informed Consent

The study will be discussed with the patient, and any patient wishing to participate must give informed consent and Authorization for Use and Release of Health and Research Study Information prior to any study-related procedures or change in treatment.

A signed, Institutional Review Board (IRB) approved, informed consent must be obtained from patients before any study specific procedures or registration for study treatment can occur.

6.2 Medical History

Medical history, such as previous treatments, procedures, and conditions will be collected during the screening period.

6.3 Physical Examination

Physical examination includes weight, HEENT (head, eyes, ears, nose, and throat), chest, cardiac, abdominal, extremities, neurologic, and lymph node examinations.

6.4 Vital Signs

Vital signs include blood pressure, heart rate, respiratory rate, and oral body temperature.

6.5 Adverse Events Assessments

6.5.1 Performing Adverse Events Assessments

All study patients who have received any dose of TKI258 will be evaluable for safety. Adverse events including laboratory adverse events deemed clinically significant by the investigator will be graded and summarized according to the National Cancer Institute Common Terminology Criteria for Adverse Events (NCI CTCAE), version 3.0.

6.5.2 Definition of an Adverse Event

An adverse event (AE) is any reaction, side effect, or other untoward medical occurrence, regardless of relationship to study drug that occurs any time from the beginning of the first study dose administration until the final study visit or early termination visit. An AE can therefore be any unfavorable and unintended sign (including an abnormal laboratory finding), symptom, or disease temporally associated with the use of a medicinal (investigational) product, whether or not related to the medicinal (investigational) product.

6.5.3 Timing

Any AE or SAE experienced by the patient from Day 1 to 30 days post last dose should be followed-up to determine if any new or ongoing drug-related AE or any SAE regardless of relationship to study drug exists. Follow-up could be conducted by site via telephone attempts.

6.5.4 Severity

Adverse-event severity is a clinical determination of the intensity of an AE. The severity assessment for a clinical AE should be completed using the NCI CTCAE (version 3.0).

6.5.5 Relationship

A determination should be made by the investigator regarding the relationship (if any) between an AE and the study drug. A causal relationship is present if a determination is made that there is a reasonable possibility that the AE may have been caused by the study drug.

6.5.6 Expectedness

Management of Symptoms Related to Castration

Treatment with androgens, estrogens, and progestin to control hot flushes is not allowed. Antidepressants are permitted for the management of hot flashes. Selective serotinin reuptake inhibitors (SSRIs) are also permitted.

Management of Persistent and Refractory Toxicity

Utilizing the NCI CTCAE (version 3.0), events which are moderate and interfere with function that are not consistent with a patient's medical history, and are refractory to medical treatment, should be investigated carefully to ensure that no other etiology is present. Study drug will be held for any toxicity events deemed definitely, probably, or possibly drug-related (such as diarrhea, hypertension, vomiting, diarrhea, and dizziness) and that are greater than grade 2. Drug will be held until severity is reduced to Grade 1 or less and then resumed daily dosing with a dose reduction of 1 capsule as outlined in section 5.2. Up to 2 dose reductions, ie, $5 \rightarrow 4$ capsules, $4 \rightarrow 3$ capsules, are allowed as outlined in section 5.2. Patients with toxicities that fail to resolve to \leq Grade 1 within 21 days will be taken off study.

Management of All Other Toxicities

Other toxicities may occur. Supportive care should be prescribed as needed. They may also be prescribed prophylactically to prevent toxicity from developing or recurring. The examples include anti-emetics for nausea/vomiting, analgesics for pain, antipyretics for fever and antidiarrheals for diarrhea. Because long-term

androgen deprivation may lead to metabolic diseases, such as glucose intolerance, hypercholesterolemia, osteoporosis, and anemia, appropriate medication may be prescribed.

Abnormal laboratory values will be only be captured as adverse events if deemed "clinically significant" by the investigator.

